8.1.5 Any procedures for the replacement of subjects

Screen failures (i.e. consented patients withdrawn for any reason up to implant of the ARGOS-SC device) will be replaced. Subjects who withdraw their consent after implantation will not be replaced.

8.2 Investigational device(s) and comparator(s)

8.2.1 Description of the exposure to the investigational device(s) or comparators, if used

The ARGOS-SC pressure sensor is intended to be permanently implanted in the subject's suprachoroidal space concomitantly with a non-penetrating glaucoma surgery of the same eye. Subjects will be exposed to transient (2 seconds) low-levels of electromagnetic energy (0.25 W) emitted by the MESOGRAPH reading device during the reading sessions, at which time their skin may also be exposed to the MESOGRAPH outer surface.

IOP measurements will be made with the ARGOS-SC system at every follow-up visit. The values obtained at Visits 02 through 04 will be compared to those obtained using GAT and at Visits 05 through 09 with GAT and if available Pascal DCT. Patients will also be requested to make daily measurements with the ARGOS-SC system in the out-patient setting.

8.2.2 Justification of the choice of comparator

GAT, considered by the medical community to be the gold standard method of IOP measurement, will be used as comparator. However, GAT actually estimates IOP based on a measurement of the force needed to applanate a predetermined area of the cornea while the ARGOS-SC sensor will be in direct contact with the aqueous humor and measure IOP directly. Consequently, differences are anticipated between the IOP values obtained with the two devices. However, trends in IOP are expected to remain the same regardless of the method used. Therefore, to assess the accuracy of the ARGOS-SC system, IOP profiles obtained with ARGOS will be compared to those obtained with GAT.

Pascal DCT is designed to eliminate some of the measurement errors in GAT that come from variations in corneal thickness and rigidity. It is believed to be closer to true IOP, especially at higher IOPs. It is also less prone to "user error".

8.2.3 Other medical devices or medication to be used

The ARGOS-SC system is the only investigational medical device that will be used during this study. No other devices or medications will be used specifically for this clinical investigation. Standard devices will be used as required for ophthalmic diagnostics and treatment procedures, including if needed glaucoma treatment.

Page 53 of 97

8.2.4 Number of investigational devices to be used

ARGOS-SC pressure sensor will be implanted in a maximum of 24 patients undergoing non-penetrating glaucoma surgery. Sites will be provided with implants at surgery. Approximately 48 devices including replacement devices, will be required for this study.

8.3 Subjects

8.3.1 Inclusion Criteria

In order to ensure that the study population is representative of the eligible patient population, the Investigator must ensure that all patients who meet the following inclusion criteria are offered enrollment in the study. The investigator may not apply any additional eligibility criteria.

Eligible subjects must meet all the following inclusion criteria:

- 1. Subjects able to understand the informed consent and willing to participate as evidenced by providing informed consent.
- 2. Patients aged \geq 18 years on the day of screening

Female subjects of childbearing potential (not surgically sterilized or more than one year postmenopausal) must have a negative pregnancy test (urine beta-hCG) within 24 hours prior to ARGOS-SC pressure sensor implantation.

- 3. Diagnosis of open angle glaucoma requiring a non-penetrating glaucoma surgery (NPGS). The medical indication for a non-penetrating glaucoma surgery must be given irrespective of the study participation. Potential study patients will be solicited for participation in the clinical trial only after the patient has given consent to the non-penetrating glaucoma operation.
- 4. Subjects able and willing to attend all scheduled visits and comply with all study procedures

8.3.2 Exclusion Criteria

Eligible subjects must not meet any of the following exclusion criteria:

- 1. Contraindications for a non-penetrating glaucoma surgery
 - Neovascular glaucoma, primary and secondary angle closure glaucoma
 - Condition after previous glaucoma surgery
 - ➢ IOP > 40 mmHg
- 2. Myopia (> -6 dpt) or hypermetropia (> +4 dpt)
- 3. Axis length < 22 mm or > 26 mm
- 4. Patient with single eye vision (monovision)
- 5. Exudative age-related macular degeneration, instable macular degeneration 30 days prior to inclusion, or macular edema
- 6. Acute retinal detachment

- 7. Uncontrolled Diabetes Mellitus (DM) with manifestation of moderate to severe nonproliferative diabetic Retinopathy (DR) or proliferative DR.
- 8. History or evidence of severe active inflammatory eye diseases (i.e. uveitis, retinitis, scleritis) in one or both eyes within 6 months prior to ARGOS-SC implantation
- 9. Ocular surgery procedure(s) (excluding selective laser trabeculoplasty and peripheral iridotomy) within 6 months (cataract surgery within 3 months) prior to ARGOS-SC implantation in the study eye that can affect the assessment of IOP by Goldmann Applanation tonometry/Pascal Dynamic Contour Tonometry
- 10. Ocular disease other than glaucoma that may affect assessment of visual acuity and/or IOP by Goldmann Applanation tonometry (e.g. choroidal hemorrhage or detachment, lens subluxation, thyroid ophthalmopathy)
- 11. Existence of other active medical eye implant and/or other active medical implants in the head/neck region
- 12. Difficulties or complications during NPGS procedure or implantation of ARGOS-SC sensor, as assessed by surgeon (e.g. perforation of trabeculo-descement's membrane, excessive aqueous filtration through TDM leading to shallow anterior chamber, excessive bleeding, choroidal detachment).
- 13. Severe generalized disease resulting in a life expectancy shorter than a year
- 14. Currently pregnant or breastfeeding
- 15. Participation in any study involving an investigational drug or device within the past 30 days or ongoing participation in a study with an investigational drug or device
- 16. Patients who are not suitable for the study based on the surgeon's evaluation (e.g. Persons affected by Parkinson's disease or essential tremor)
- 17. Patients unable or unwilling to understand or comply with required study procedures
- 18. Patients with psychiatric disorders influencing their judgement or autonomy
- 19. Subject and/or an immediate family member is an employee of the investigational site directly affiliated with this study, the sponsor or the contract research organization.
- 20. Enrollment of the fellow eye in this clinical study

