and standard clinical procedures. If it becomes apparent during the surgery that the subject is not a suitable candidate for the ARGOS-SC pressure sensor implant, the subject will be removed from the study and returned to standard of care.

At Visit 01, data will be collected regarding:

General

- Implantation procedure questionnaire (surgeon)
- AE/ADE/SAE/SADE/UADE
- Concomitant medication
- Device deficiency

Follow-up (V02 to V09)

The follow-up period after surgery will consist of 8 visits (Day 1 until Day 360). The examinations performed at each visit are listed without mentioning the single visit in parentheses. Examinations that are carried out only at distinct visits are indicated in parentheses. The follow-up visits will include:

General

- VQoL questionnaire (V06, V07, V09)
- Visual acuity (EDTRS)
- Perimetry (V06, V07, V09)
- External Eye Photography (V04-V09)
- Heidelberg Engineering ANTERION[®] (location of ARGOS-SC)(V04-V09), if available
- User acceptance questionnaire (investigator) (V09)
- User acceptance questionnaire (patient) (V09)
- AE/ADE/SAE/SADE/UADE
- Concomitant medication
- Device deficiency

Anterior Segment

- Slit-lamp biomicroscopy
- Optical coherence tomography (OCT) of cornea and anterior chamber (V04-V06)
- Gonioscopy (V06, V07, V09)

Posterior segment

• Slit lamp biomicroscopy

	 Optical coherence tomography (OCT) of macula and optic nerve (V06, V07, V09)
	 Fundus photography (V06, V07, V09)
	IOP measurements
	• GAT
	 Pascal DCT (V05-V09) (if available)
	ARGOS-SC system measurements
	 Optional: 24-hours measurements inpatient with ARGOS-SC and GAT (V06, V07, V09)
	ARGOS-SC system self-measurement at home
Data Analysis	Primary Endpoint
and Statistics	Performance
	- Level of Agreement between measurements made using GAT, Pascal DCT and the ARGOS-SC system from V02 (day 1) through V09 (day 360).
	Secondary Endpoints
	Safety
	 Number of patients experiencing a device-related SAE (SADE) at any time during implantation and in the first 12 months (Day 0 to Day 360) following it
	 Incidence, nature, severity and seriousness of observed adverse events and adverse device events at any time during implantation and in the 12 months following it
	Performance
	- Repeatability of the ARGOS-SC measurement
	 Incidence, nature and seriousness of observed device malfunctions during implantation and in throughout a 12 months follow-up period.
	Utility

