6.6 Possible Alternative Treatments

Only patients who require and have already consented to non-penetrating glaucoma surgery will be contacted regarding participation in this study. They will undergo the same non-penetrating glaucoma surgery regardless of whether they participate in the study or not. The only differences in their treatment will be any adaptations to the surgery required by the ARGOS-SC implant related procedures, such as placement of the ARGOS-SC implant, access to the suprachoroidal space and a slightly longer surgery time.

Treatment decisions during the follow-up period will be based primarily on IOP measurements obtained using conventional tonometry. Abnormalities in IOP detected through measurements obtained with the ARGOS-SC device may however result in additional clinic visits for further diagnosis. If potential subjects choose not to participate in the study, their IOP levels will be monitored using their physician's preferred method.

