8.1.3.2 Secondary endpoints

Safety

- Number of patients experiencing a device-related SAE (SADE) at any time during implantation and in the first 12 months (Day 0 to Day 360) following it.
- Incidence, nature, severity and seriousness of observed adverse events and adverse device events at any time during implantation and 12 months following it.

Performance

- Repeatability of the ARGOS-SC measurement
- Incidence, nature and seriousness of observed device malfunctions during implantation and in the 12 months follow-up

Utility

- User acceptance of the ARGOS-SC implantation procedure by means of evaluation of implantation procedure questionnaires (investigators)
- User acceptance of the ARGOS-SC system at the investigational site by means of evaluation of patient acceptance questionnaires (by investigators)
- User acceptance of the ARGOS-SC system at home by means of evaluation of patient acceptance questionnaires (patients)
- Daily IOP self-measurement profiles (patients)

8.1.4 Equipment to be used to assess the clinical investigation variables and arrangements for monitoring maintenance and calibration

Sites will use their own diagnostic devices. The study monitor will verify that the sites maintain and calibrate these devices on a regular basis.

Page 52 of 97

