9.4 Expected drop-out rates

The drop-out rate for this study following implantation is expected to be low. The ARGOS-SC is intended to remain in situ and the patient population generally requires close follow-up care by the ophthalmologist. Subjects who do not undergo implantation of an ARGOS-SC will be replaced.

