9.11 Datasets to be analyzed

9.11.1 Safety set

The safety population comprises all subjects for whom ARGOS-SC pressure sensor implantation was attempted, defined as introduction of the ARGOS-SC pressure sensor into the eye, whether or not the implantation was successful.

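### The safety set starts when the sensor enters the eye, so a complication at an earlier implant-specific step that stops the implantation drops out of the safety tables, and the 9.5 pass rule may miss other intra-operative SADEs

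*Protocol*

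**What the plan says.** **Exclusion and replacement.** Criterion 12 (Protocol 8.3.2, repeated in SAP 2.5) excludes for "Difficulties or complications during NPGS procedure or implantation of ARGOS-SC sensor, as assessed by surgeon". Its examples are perforation of the trabeculo-Descemet membrane (TDM), over-filtration with a shallow anterior chamber, bleeding and choroidal detachment. The synopsis (Surgery, V01) says that if the patient proves unsuitable during the operation, "the subject will be removed from the study and returned to standard of care". Protocol 8.1.5 adds: "Screen failures (i.e. consented patients withdrawn for any reason up to implant of the ARGOS-SC device) will be replaced". Protocol 8.3.3.3 repeats the replacement rule for withdrawal before implantation, and 9.4 says: "Subjects who do not undergo implantation of an ARGOS-SC will be replaced".

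**Who is counted.** Protocol 9.11.1 and SAP 3.7 admit to the safety set patients in whom implantation was attempted, "defined as introduction of the ARGOS-SC pressure sensor into the eye, whether or not the implantation was successful". The AE tables (Protocol 9.1.3) and all safety analyses (SAP 3.7) use that set.

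**What happens before the sensor enters.** Protocol 4.7, 8.3.14.1 and 8.3.14.2 place two steps after the pressure-lowering part of the surgery and before insertion: viscoelastic separation of sclera from choroid and, where needed, a wider flap or an extra incision for the sensor. Section 6.6 lists the adaptations required by the implant, "such as placement of the ARGOS-SC implant, access to the suprachoroidal space".

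**Endpoint and pass rule.** The endpoint in 8.1.3.2 is "Number of patients experiencing a device-related SAE (SADE) at any time during implantation" and through the following 12 months. The rule in 9.5 allows at most one SADE patient among the 24 and refers to SADEs in follow-up. The synopsis describes follow-up as Day 1 to Day 360.

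**The concern.** The study's stated purpose includes the safety and feasibility of the surgical implantation, so the events of most interest are those of the implantation step. Three of the examples in criterion 12 (TDM perforation, shallow anterior chamber, choroidal detachment) are also AEs of particular interest in Protocol 7.3. Section 6.3 accepts that adding the device may make such events more likely or more severe.

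The step just before insertion is not a formality. In the second rabbit study (4.8.2.1) the surgeon had difficulty forming the suprachoroidal cavity, and the protocol gives this as one likely reason for the mechanical damage seen, while expecting the step to be easier in human eyes.

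If a patient has such an event and the implantation is stopped, the plan replaces that patient with another. The SADE count and the AE incidences to be compared with the literature on standalone surgery then describe a selected group. The surgeon, who is unmasked, makes the selection.

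**Working it through.** **Step 1. Follow one complication through the plan, by when it occurs.**

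| Time of event | Criterion 12 and replacement | In safety set? | Counted in 9.5? |
|---|---|---|---|
| A. Pressure-lowering surgery, before any implant-specific step | Excluded, replaced | No | No |
| B. Viscoelastic separation or widening for the sensor; implantation stopped | Excluded, replaced | No | No |
| C. Sensor introduced, then taken out in the same operation | Criterion 12 names it; 9.4 may replace | Yes | Unclear |
| D. Implantation completed | No text replaces the patient | Yes | Intra-operative SADE: not on a literal reading |

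Row A is reasonable: the device is not yet involved. Row B is the gap: 6.6 treats access to the suprachoroidal space as implant-related and 8.1.3.2 covers the whole implantation, yet the patient is outside every safety table. Rows C and D are kept in the AE tables. They are doubtful only in 9.5, because that rule refers to follow-up and to a fixed 24 patients.

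**Step 2. Recording.** AE recording starts at implantation in Protocol 8.3.13.4, and so does SAE reporting to the sponsor in 11.4. Sections 8.3.17 and 11.3 start AEs at consent. Whether a row B event must be reported depends on which section is followed and on when implantation is taken to begin. The eight follow-up visits are for patients who receive an implant (8.1.1), and the end-of-study assessments are for implanted patients who stop early (8.3.3.3).

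**Step 3. The plan's own figure.** The 24 patients and the limit of one cannot be rebuilt: neither document gives a SADE rate, and the sample-size file is only cited. What the rule does follows from the binomial:

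P(at most 1 of 24) = (1−p)^24 + 24p(1−p)^23

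This gives 91.7% at p = 2%, 66.1% at 5%, 29.2% at 10% and 10.6% at 15%.

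**Step 4. One or two uncounted cases.** Suppose one SADE is counted among 24, and k further SADE patients were replaced. The apparent rate is 1/24 = 4.2%. The rate over all attempts is (1+k)/(24+k): 2/25 = 8.0% for k = 1 and 3/26 = 11.5% for k = 2. With k = 1 there are already two SADE patients, above the limit of one.

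**Step 5. Range under assumed rates.** Let a be the intra-operative SADE rate, b the follow-up SADE rate and f the share of intra-operative SADE patients removed and replaced. All three are assumptions. The total rate is t = 1 − (1−a)(1−b). Among the 24 counted patients it becomes (t − fa)/(1 − fa). If 9.5 did count intra-operative SADEs, the chance of passing would be:

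| a, b | t | f = 0 | 25% | 50% | 75% | 100% |
|---|---|---|---|---|---|---|
| 5%, 2% | 6.9% | 50.0% | 59.7% | 70.5% | 81.5% | 91.7% |
| 10%, 2% | 11.8% | 20.7% | 31.8% | 47.9% | 69.2% | 91.7% |
| 15%, 4% | 18.4% | 4.9% | 10.1% | 20.8% | 41.3% | 75.1% |

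For the safety tables, f is limited to the row B share, which the documents do not give. The table shows direction and range and is not an estimate.

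**The case against.** The strongest reply is that the plan already protects most of what matters. The safety set keeps failed implantations once the sensor has entered the eye. Section 8.3.3.3 does not replace patients who leave after implantation. It also follows a patient discontinued for an AE related to a study device or procedure until the event resolves or stabilises, and 11.3 and 12.13 do the same for SAEs. Enrolment halts at each serious device event (synopsis), a DSMB reviews SAEs and SADEs (11.7), reasons for screen failure are tabulated (9.1.2), and SAP 4.5 reports surgical complications.

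Much of this stands, and it rules out some stronger readings. A reader might infer that criterion 12 strips the endpoint of implantation complications in general, or that patients harmed in a completed implantation are replaced. The documents support neither. A reader might also infer that a row B patient is abandoned with nothing but operative notes. The text on data up to that point describes additional information, and the event follow-up above can apply.

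It is equally tempting to assume a rate of serious complications that stop implantation and to read the chance of two or more in 24 as the chance that the trial should have failed. Such a rate would include events after sensor introduction, which the safety set keeps, and 9.5 read literally ignores intra-operative SADEs in every patient.

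The safeguards do not close the gap itself. Following an event to resolution does not put the patient in the safety set, in the AE tables or in the denominator of 9.5. The enrolment halt and the DSMB review depend on the event being reported, and the start of reporting is in conflict.

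**Conclusion.** The point holds in a limited form. A patient whose complication at an implant-specific step before sensor introduction stops the implantation is removed, replaced and absent from the AE and SADE tables, although the endpoint covers the whole implantation. Separately, the wording of 9.5 may leave out intra-operative SADEs in any patient, and failed attempts that were replaced.

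Both effects favour the device. Their size cannot be derived, because the documents give no rate for such events and no share occurring before introduction. Since the limit is one patient, a single uncounted SADE is enough to matter: 1/24 reported against 2/25 over all attempts. This conclusion rests on reading implantation as including the steps made solely for the sensor, as 6.6 does.

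**What to change.** 1. In Protocol 9.11.1 and SAP 3.7, define an attempted implantation as the start of the first implant-specific step: suprachoroidal access, viscoelastic separation, or widening of the opening for the sensor.
2. Keep every attempted patient in the safety set, replaced or not, and collect AEs to Day 360 if the patient agrees. Replacements may still join the agreement analysis.
3. In 9.5, count SADEs from the start of implantation to Day 360, as in 8.1.3.2, with all attempted patients in numerator and denominator. Changing the safety set alone would leave the follow-up restriction in place.
4. Report every intra-operative exclusion with its timing and events.
5. Reconcile criterion 12, the synopsis text on removal during surgery, and 8.1.5, 8.3.3.3, 9.4 and 9.5. State how a patient is counted and followed once implant-specific steps have begun. Settle the start of AE and SAE recording between 8.3.13.4 and 11.4 on one side and 8.3.17 and 11.3 on the other. None of this need alter the surgeon's freedom to stop.

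The cost is protocol and SAP wording and follow-up of the few patients with an aborted implantation. The SADE count may look less favourable, and the safety denominator may slightly exceed 24.

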8.3.3 Discontinuation or Withdrawal Criteria

8.3.3.1 Study stopping rules

The study may be discontinued at any time for administrative reasons; if new negative data about the investigational device resulting from this or any other study becomes available; and/or on the recommendation of the sponsor, the investigators, and/or the EC or regulatory authorities.

Page 55 of 97

If the study is prematurely terminated or suspended, the sponsor will promptly inform the investigators, the Regulatory Authorities and the ECs of termination or suspension and the reason behind it. If the study is prematurely terminated for any reason, the investigator should promptly inform the site's study subjects and assure they receive appropriate therapy and/or follow-up.

The study can be terminated at any time for any reason by the sponsor.

8.3.3.2 Screen Failures

Screen failures are subjects who have signed the informed consent form and either fail to meet eligibility criteria for enrollment e.g. they do not meet one or more of the inclusion criteria or do meet one or more of the exclusion criteria, and subjects who revoke their consent and agreement preoperatively. Such subjects will return to standard treatment.

The only data collected on subjects who fail to meet eligibility criteria prior to surgery will be the date of their screening visit, the date they gave informed consent and reason they are a screen failure. This data will be entered on the screening summary page in the CRF.

8.3.3.3 Premature subject withdrawal

Subjects will be informed that they have the right to withdraw from the study at any time. The investigator must determine whether voluntary withdrawal is due to a cause that could raise safety concerns.

All subjects who withdraw from the study after implantation and before completing the follow-up visits per protocol will be considered to be drop-outs. Subjects who drop-out or are withdrawn after implantation will not be replaced. Unless the patient revokes his/her permission to use it, any data collected up to the point of the patient's withdrawal will be included in the analysis. The data of all subjects who undergo implantation of the ARGOS-SC pressure sensor will be included in the efficacy analysis under the Full Analysis Set.

A subject will be withdrawn for any of the following reasons:

• The subject withdraws informed consent.

- It is determined during NPGS surgery that the subject is not feasible for ARGOS-SC pressure sensor implantation. Subjects withdrawn before implantation of the sensor will be replaced.
 For subjects determined to be ineligible during NPGS surgery, additional information will be collected about the procedure up to that point.
- The ARGOS-SC pressure sensor must be removed for any reason.

If the subject permits, all end-of-study assessments indicated in the visit schedule will be performed for implanted early discontinuing subjects.

Any subject who has been discontinued from the study because of an AE related to a study device or procedure will be followed as deemed appropriate by the investigator until resolution or stabilization of the event. This will be documented in the medical chart and in the CRF. Any subject who has been discontinued from the study because of an AE not related to a study device or procedure will be followed as deemed appropriate by the investigator.

The investigator will classify the termination reason of each subject at the end of the study in the termination page of the CRF according to the following:

- AE
- Non-compliance with clinical investigation plan (CIP)
- Lost to follow up
- Voluntary withdrawal not for AE
- Other reason

The choice of keeping the implant or letting the implant be retrieved will be offered to the participating patients.

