The purpose of this clinical investigation, which will follow up all patients who receive an ARGOS-SC device for 12 months after implantation, is to determine the safety of implantation of the ARGOS-SC in conjunction with a non-penetrating glaucoma surgery, as well as to explore the agreement of the IOP measured with ARGOS-SC system and GAT and DCT (dynamic contour tonometry).

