6.4 Risks and Benefits associated with the participation in the clinical investigation

- ARGOS-SC system associated risks As described in Section 6.2, a full risk analysis was performed during the development of the ARGOS-SC system to anticipate and eliminate or at least minimize all foreseeable ARGOS-SC system-related risks. However as with any new device it is possible that unknown risks remain that will only become apparent as more experience is gained with the device. The safety of the study patients is of paramount importance and will be monitored throughout the study at all times. If at any time a safety issue arises that is thought to be related to the ARGOS-SC implant, to the specific procedures necessary to implant it, or to its use to measure IOP, appropriate measures will be initiated immediately to minimize risk to current and future study patients. All investigators will be kept informed of such issues. The ARGOS-SC was designed to be able to remain in the eye even in the event of failure. If it must be removed, for example due to adverse effects, the risks of removal correspond to those associated with implantation.
- Data Privacy Risks Health data about study patients will be collected and transferred to an electronic database. Although all currently required methods will be used to protect patients' privacy, the security of such databases can never be completely ensured. For this reason, no information that can identify study patients other than the pseudonymising Subject ID will be used on the database or on any study documentation other than the patient log, which will remain at the site. Potential patients will be informed of the data privacy policy during the informed consent process.
- Because of patients' vulnerable nature, there is a risk that they may either feel obligated to participate in the study or that their knowledge of the study may influence their decision whether

or not to undergo NPGS at this time. To mitigate these risks, only patients who have already consented to NPGS will be informed of the study and all potential study patients will be told explicitly that they are free to choose not to participate, and that refusing will not affect their treatment except in regards to the ARGOS-SC system.

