9.7 Criteria for termination of the clinical investigation

The participation of an individual site in the study will be discontinued if the sponsor, the investigator or the responsible ethics committee deems it necessary for any reason.

The complete study will be discontinued:

- If the sponsor and/or any responsible regulatory authority or ethic committee judges it necessary for any reason. See also Section 8.3.3 Discontinuation or Withdrawal Criteria Early Patient Withdrawal and Section 12.11 Criteria for Suspension and Premature Termination of Study
- If, throughout the course of the study, the DSMB comes to the conclusion that further implantation of the ARGOS-SC pressure sensor would subject study patients to undue risk

Patients who already have an ARGOS-SC pressure sensor implanted by the time of premature termination will continue to be followed up. If the study is discontinued for safety reasons it will be

proven whether explantation of all ARGOS-SC sensors deems necessary or follow-up of patients is sufficient.

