12.13 Subject follow-up requirements

All pregnancies will be followed up to birth. All on-going AEs will be followed-up until resolution or until 7 days after the last subject has been discharged from the study. All SAEs will be followed-up until resolution or stabilization.

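### Sensor removal ends study participation, so explanted subjects have no scheduled search for new adverse events up to Day 360

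*Protocol*

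**What the plan says.** Protocol 8.3.3.3 gives the reasons for which a subject is withdrawn. One of them is "The ARGOS-SC pressure sensor must be removed for any reason". The provisions that still apply after withdrawal are these:

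- With the subject's agreement, "all end-of-study assessments indicated in the visit schedule will be performed for implanted early discontinuing subjects" (8.3.3.3).
- A subject discontinued for an AE related to the device or a study procedure "will be followed as deemed appropriate by the investigator until resolution or stabilization of the event". If the AE is unrelated, follow-up is left to the investigator's judgement (8.3.3.3).
- "All SAEs will be followed-up until resolution or stabilization" (12.13). Other ongoing AEs are followed until they resolve or until 7 days after the last subject is discharged (11.3 and 12.13).

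Other sections assume full follow-up. Section 3.3 describes the investigation as one "which will follow up all patients who receive an ARGOS-SC device for 12 months after implantation", and 8.1.1 has every implanted patient attend eight follow-up visits. Section 8.1.3.2 counts patients with a SADE "at any time during implantation and in the first 12 months (Day 0 to Day 360) following it" and reports AEs and ADEs over the same 12 months. Under 9.5, success requires no more than one of 24 patients with a SADE.

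On removal itself, 6.4 states that "the risks of removal correspond to those associated with implantation". Section 8.3.14.3 describes the explantation procedure and gives no follow-up after it.

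**The concern.** In a first-in-human study of a permanent implant, subjects whose sensor is removed are among the most informative about device harm. Removal is a second procedure in the suprachoroidal space, which the protocol itself rates as risky as implantation. If removal also ends participation, the scheduled means of finding later events ends when that second procedure has just been done. A subject with no SADE recorded up to that point would still stand in the safety count as a subject without a SADE. Any resulting under-count would depend on outcome and would favour the device.

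**Working it through.** The plan states no explantation rate, no expected SADE rate and no figure for observation after removal, so there is no planned figure to reproduce.

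**Step 1. What looks for new events.** Under 11.3, new AEs come from a question asked at each visit, from direct observation and from spontaneous reports. After withdrawal no visits remain beyond the one end-of-study assessment. Spontaneous reporting is not ruled out, but nothing is scheduled.

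**Step 2. What remains, by reason for removal.**

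| Reason for removal | End-of-study assessments | Follow-up of the known event | Scheduled search for new events to Day 360 | Can a later SADE change the patient-level count? |
|---|---|---|---|---|
| Event that is itself a SADE | If subject agrees | To resolution or stabilization | None | No, already counted |
| Related AE, not serious | If subject agrees | To resolution or stabilization | None | Yes, if no earlier SADE |
| Unrelated AE | If subject agrees | Investigator's judgement; SAEs to resolution or stabilization | None | Yes, if no earlier SADE |
| No AE (patient choice, device deficiency) | If subject agrees | No causing event to follow | None | Yes, if no earlier SADE |

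The last row is foreseeable. Section 8.3.3.3 offers participants the choice of having the implant retrieved (timing not stated), and SAP 4.6.2 lists, among the consequences of a sensor deficiency, an item that appears to mean explantation. Protocol 11.3.4 also records device removal and study withdrawal as separate actions, whereas 8.3.3.3 makes the first force the second.

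**Step 3. Scheduled observation lost.** Share lost = (360 − removal day)/360, with visit days from Table 1.

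- Day 30: 330/360 = 92%, with V06 to V09 lost.
- Day 90: 270/360 = 75%, with V07 to V09 lost.
- Day 180: 180/360 = 50%, with V08 and V09 lost.

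**Step 4. How the analysis treats these subjects.** Protocol 9.10 analyses observed cases, replaces nothing, and evaluates early terminators like completers. SAP 3.7 keeps every subject with attempted implantation in the safety set. Neither document adjusts for shortened observation. It follows by inference that an explanted subject with no recorded SADE counts as having none.

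**Step 5. Sensitivity of the at-most-one rule.** All inputs here are assumed. Two of 24 subjects are explanted with no earlier SADE, the other 22 have a 5% SADE risk, and each explanted subject has post-removal SADE risk q.

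- Post-removal SADEs all missed: P(pass) = 0.95^22 + 22 × 0.05 × 0.95^21 = 0.3235 + 0.3746 = 0.698.
- All captured: P(pass) = 0.3235 × (1 − q²) + 0.3746 × (1 − q)².
  - q = 10%: 0.624
  - q = 25%: 0.3033 + 0.2107 = 0.514
  - q = 50%: 0.336

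These figures show direction and sensitivity only.

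**The case against.** Three stronger readings are tempting, and the documents do not support them.

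- **That safety follow-up stops at removal.** It does not. The end-of-study assessments, the follow-up of a related causing AE, and the rules in 11.3 and 12.13 for known AEs and SAEs all continue. What is missing is the scheduled search for new events. The percentages in Step 3 are therefore scheduled observation lost, not time with no safety information at all.
- **That any event missed after explantation could change the pass/fail result.** The criterion counts patients, not events. Under 11.2.2 and 11.2.3, a device-related event that needs hospitalization, or surgery to prevent permanent impairment, is already a SADE. Many medically necessary removals would therefore concern subjects already counted, and nothing later changes their status.
- **That 9.7 contradicts 8.3.3.3.** Section 9.7 concerns termination of the whole study: "Patients who already have an ARGOS-SC pressure sensor implanted by the time of premature termination will continue to be followed up". It then leaves open whether explantation of all sensors is needed or follow-up is sufficient. It does not say that explanted subjects leave follow-up. This is an ambiguity.

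It can also be said that 3.3 is background text, that general follow-up statements normally give way to withdrawal rules, that removal is expected to be rare (9.4 intends the sensor to stay in place, and 6.4 says it can remain after failure), and that this is an exploratory study with safety as a secondary objective. These points lower the severity. They do not close the gap, because 8.1.1 makes the same commitment in the design section and the SADE limit is one of the two success criteria in 9.5.

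**Conclusion.** The point holds in a limited form. Mandatory withdrawal on removal leaves no scheduled visits and no active collection of new events, including late complications of the explantation, up to Day 360. That conflicts with the 12-month, eight-visit follow-up in 3.3 and 8.1.1, and it leaves the safety endpoints in 8.1.3.2 incompletely observed for explanted subjects.

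The effect on the SADE count and the 9.5 criterion is confined to subjects explanted without a prior SADE. The incidence endpoint for AEs and ADEs is affected for all explanted subjects. The gap is widest where no AE prompted the removal. How much this matters depends on how many sensors are removed, and when, and the documents give neither. The conclusion rests on reading withdrawal in 8.3.3.3 as ending the scheduled visits, which is the natural reading because no later visit is provided for. Severity: should-fix.

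**What to change.** Reconcile 3.3, 8.1.1, 8.1.3.2, 8.3.3.3, 8.3.14.3, 9.5 and 9.7 by separating end of device use from withdrawal from the study:

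1. In 8.3.3.3, record sensor removal as end of device use. Reserve withdrawal from the study for subjects who withdraw consent or leave for another listed reason.
2. Keep explanted subjects who still consent on the existing visit schedule to V09 for safety data collection, omitting the ARGOS-SC readings. Refer to this in 8.3.14.3.
3. State in 8.1.3.2 and 9.5 that events after explantation, including those of the explantation procedure, count in the Day 0 to Day 360 safety endpoints, with the usual assessment of seriousness and device relationship.
4. Clarify that the continued follow-up in 9.7 also covers explanted subjects.

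This is a change of protocol wording. The visits are already planned for every subject, so the downside is a small visit burden for the few who are explanted. It concerns data collection only. No rule is proposed on when or whether a sensor should be removed.
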